4.2.3.1. Reverting to Accelerated Dose Titration

Subsequent cohorts may revert to one subject per cohort in either of the following scenarios:

- Two additional subjects are added at the dose where the non-disease-related ≥ Grade 2 toxicity is seen in the initial subject, and no non disease-related Grade 2 or higher toxicity is seen in either of the two new subjects.
- All subjects treated at next higher dose level do not have a non-disease-related Grade 2 or higher toxicity.

However, the dose escalation may continue with multiple subjects per cohort per the clinical judgment of the Medical Monitor in consultation with the investigators. The

decision on the number of subjects will be documented in writing together with the dose escalation decision and the rationale.

4.2.4. Dose Escalation Decisions and Determination of MTD

4.2.4.1. Dose-Limiting Toxicity

An event is considered to be a dose-limiting toxicity (DLT) if the event occurs within the first 21 days of treatment and meets the criteria listed in Table 1, unless it can be clearly established that the event is unrelated to treatment.

Toxicity	DLT Definition
Hematologic	 Grade 3 neutropenia (absolute neutrophil count [ANC] <1000/mm³) for ≥5 days or Grade 4 neutropenia of any duration Grade 3 or greater febrile neutropenia Grade 4 or greater anemia of any duration Grade 4 thrombocytopenia (platelets <25,000/mm³), or Grade 3 thrombocytopenia with bleeding
Non-hematologic	 Alanine aminotransferase (ALT) >3x upper limit of normal (ULN) + bilirubin ≥2xULN (>35% direct) or ALT between 3-5 X ULN with bilirubin < 2xULN but with hepatitis symptoms^a or rash (See Section 5.4.5 for Liver Stopping Criteria) Grade 3 nausea, vomiting or diarrhea that does not improve within 72h despite appropriate supportive treatment(s) Grade 4 or greater nausea, vomiting, or diarrhea Grade 3 hypertension^b (uncontrolled despite addition of up to 2 antihypertensive medications) Grade 4 or greater clinically significant non-hematologic toxicity per National Cancer Institute - Common Terminology Criteria for Adverse Events (NCI- CTCAE), v4 except toxicities listed in Section 4.2.4.2.
Other	 Inability to receive at least 80% of scheduled doses in the DLT observation period due to toxicity^c Grade 2 or higher toxicity that occurs beyond 21 days which in the judgment of the investigator and GlaxoSmithKline (GSK) Medical Monitor is considered to be a DLT

 Table 1
 Dose-Limiting Toxicity Criteria

Toxicity Grading based on NCI-CTCAE v4

a. New or worsening symptoms believed to be related to liver injury (such as fatigue, nausea, vomiting, right upper quadrant pain or tenderness, or jaundice) or believed to be related to hypersensitivity (such as fever, rash or eosinophilia)

- b. Grade 3 hypertension adequately controlled by antihypertensive medication(s) is not considered to be a DLT.
- c. Subjects unable to receive at least 80% of scheduled doses for reasons other than toxicity (e.g., acute illness, disease progression) will not be evaluable for DLT purposes and will be replaced in the cohort

Table 1 provides a list of protocol-defined DLTs; it does not provide guidelines for management of these toxicities. In appropriate clinical circumstances, resumed dosing after a DLT (at a reduced dose level) may be considered after discussion between the

investigator, medical monitor, and GSK medical governance (as necessary). For management of liver toxicity, please refer to Section 5.4.5. For management of cardiac toxicity, see Section 5.4.6. For management of all other toxicities, see Appendix 2.

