4.2. Part 1: Dose Escalation

The primary objective of Part 1 is to identify the MTD of GSK3326595 when administered orally in subjects with solid tumors. As described in Section 4.7, dosing will start at 12.5 mg once daily and escalate until the MTD is reached. In Part 1, any subject who prematurely discontinues therapy during the DLT observation period for reasons other than a DLT will be replaced by additional subject(s) assigned to the same dose level.

. Subjects will also be enrolled at or about the RP2D into a food effect and relative bioavailability sub-study (Section 4.2.6) to evaluate the effects of food and GSK3326595 formulation on GSK3326595 pharmacokinetics.

Dose escalation will be conducted in two stages: dose exploration (Section 4.2.2) and MTD confirmation (Section 4.2.3). Details common to both stages, including DLT definitions and dose increments, are described in Section 4.2.4.

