4.2.3. Determining the MTD

Starting with the first cohort exhibiting a non disease-related \geq Grade 2 toxicity (except for those listed in Section 4.2.4.2), a modified Toxicity Probability Interval (mTPI) design will be implemented (Figure 4-1) [Ji, 2010]. Cohorts will be recruited in blocks of three subjects. The maximum number of subjects assigned to any single dose will be at the discretion of the Sponsor in consultation with the investigators.

The design assumes (i) approximately 38 subjects will complete the DLT evaluation period and (ii) the true underlying toxicity rate for GSK3326595 falls within the range from 25% to 35% and centered at 30%. The monitoring rules guiding dose escalation are provided in Figure 4-1. Columns provide the numbers of subjects treated at the current dose level, and rows provide the corresponding numbers of subjects experiencing toxicity. The entries of the table are dose-finding decisions (i.e., E, S, and D) representing escalating the dose, staying at the same dose, and de-escalating the dose. In addition, decision U means that the current dose level is unacceptable because of high toxicity and should be excluded from the trial. For example, when one of three subjects experiences toxicity, the decision can be located at row 1 and column 3, which is S - tostay at the current dose level. Consequently, the next cohort of subjects will be treated at the same dose level currently being used. If zero of three subjects experiences toxicity, the decision is at row 0 and column 3, which is E - to escalate. Thus, the next cohort of subjects will be treated at the next-higher dose level. If three of three subjects experiences toxicity, the decision is DU - to de-escalate to the next-lower dose level and exclude the current dose from the trial, because the high toxicity level is unacceptable.

During dose escalation, when 2 or more subjects are enrolled in a cohort, no two subjects may start treatment on the same day. This staggered dosing start is not required for subjects enrolling at previously cleared doses or for subjects enrolled in Part 2 of the study.

Figure 4-1 Dose-finding spreadsheet of the modified toxicity probability interval (mTPI) method

										Νι	ımt	ber	of p	oati	ent	s tr	eate	ed a	at c	urr	ent	do	se								
		1	2	3	4	5	6	7	8	9	10	11	12	13	14	15	16	17	18	19	20	21	22	23	24	25	26	27	28	29	30
	0	Е	E	E	Е	E	E	E	E	E	E	E	E	E	E	E	E	E	E	E	E	E	E	E	E	E	E	E	E	Е	E

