14.6. Appendix 6: Liver Safety Required Actions and Follow-up Assessments

Phase I/II liver chemistry stopping and increased monitoring criteria have been designed to assure subject safety and to evaluate liver event etiology (in alignment with the FDA premarketing clinical liver safety guidance) [www.fda.gov, 2009].**Phase I/II liver chemistry stopping criteria and required follow up assessments**

	Liver Chemistry Stoppir Subject with ent	ng Criteria – Liver Stopping Event ry criteria ALT≤ 2.5 x ULN	
ALT-absolute	$ALT \ge 5xULN$		
ALT Increase	ALT \geq 3xULN persists	for \geq 4 weeks	
Bilirubin ^{1, 2}	$ALT \ge 3xULN$ and bili	rubin \ge 2xULN (>35% direct bilirubin)	
INR ²	ALT \ge 3xULN and INF	R>1.5, if INR measured	
Cannot Monitor	ALT \ge 3xULN and c	annot be monitored weekly for 4 weeks	
Symptomatic ³	ALT \geq 3xULN associated with symptoms (new or worsening) believed to be related to liver injury or hypersensitivity		
	Liver Chemistry Stopping Criteria – Liver Stopping Event		
Including subj	jects with documented liv entry criteria AL	ver metastases/tumor infiltration at baseline AND T>2.5 x ULN but ≤5 x ULN	
ALT-absolute	solute Both $ALT \ge 5xULN$ and $\ge 2x$ baseline value		
ALT Increase	Both ALT \ge 3xULN and \ge 1.5x baseline value that persists for \ge 4 weeks		
Bilirubin ^{1, 2}	ALT \ge 3xULN and bilirubin \ge 2xULN (>35% direct bilirubin)		
INR ²	ALT \ge 3xULN and INR>1.5, if INR measured		
Cannot Monitor	Both ALT \ge 3xULN and \ge 1.5x baseline value that cannot be monitored for 4 weeks		
Symptomatic ³	Both ALT \ge 3xULN and \ge 1.5x baseline value associated with symptoms (new or worsening) believed to be related to liver injury or hypersensitivity		
Required A	ctions and Follow up Ass	essments following ANY Liver Stopping Event	
	Actions	Follow Up Assessments	
Immediately discontinue study Viral hepatitis serology ⁴		 Viral hepatitis serology⁴ 	

Liver Chemistry Stopping Criteria – Liver Stopping Event			
Subject with entry criteria ALT≤ 2.5 x ULN			
 treatment Report the event to GSK within 24 hours 	 Only in those with underlying chronic hepatitis B at study entry (identified by positive hepatitis B surface antigen) quantitative hepatitis B DNA and hepatitis delta antibody⁵ 		
 Complete the liver event CRF and complete an SAE data collection tool if the event also meets the criteria for an SAE² Perform liver event follow up 	Blood sample for pharmacokinetic (PK) analysis, obtained 2 days after last dose ⁶		

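### Part 1 DLT definition: the symptomatic-ALT route stops at 5 x ULN, so a worse liver event late in the 21-day window can be missing from the mTPI count

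*Protocol*

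**What the plan says.** **DLT definition.** Under Protocol Section 4.2.4.1, a Part 1 event is a DLT if it falls in the first 21 days and meets Table 1, unless it is clearly unrelated to treatment. Table 1 has two liver routes. The first is ALT above 3 x ULN with bilirubin at or above 2 x ULN (over 35% direct). The second is "ALT between 3-5 X ULN with bilirubin < 2xULN but with hepatitis" symptoms, or with rash. The same cell points to Section 5.4.5 for the liver stopping criteria. The general non-hematologic row begins at Grade 4. Two further rows could matter: "Inability to receive at least 80% of scheduled doses in the DLT observation period due to toxicity", and a judgement row for "Grade 2 or higher toxicity that occurs beyond 21 days which in the judgment of the investigator" and the medical monitor is a DLT. The text below the table adds: "For management of liver toxicity, please refer to Section 5.4.5".

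**Stopping rules (Appendix 6).** With entry ALT up to 2.5 x ULN, treatment stops at once at ALT of 5 x ULN or more, or at 3 x ULN or more "associated with symptoms (new or worsening) believed to be related to liver injury or hypersensitivity". With liver metastases and entry ALT above 2.5 x ULN, the symptomatic stop needs ALT of at least 3 x ULN and at least "1.5x baseline value associated with symptoms (new or worsening) believed to be related to liver injury or hypersensitivity".

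**Replacement.** Section 4.2 says that "any subject who prematurely discontinues therapy during the DLT observation period for reasons other than a DLT will be replaced by additional subject(s"). Section 4.2.2 and footnote c of Table 1 are narrower: they replace subjects who miss the 80% mark for reasons other than toxicity.

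**Part 3.** Section 4.4.4.1 expressly counts drug-related liver toxicity that meets the Section 5.4.5 stopping criteria.

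**The concern.** A toxicity rule should not score a worse event below a milder one. Here a subject with symptoms and ALT of 4 x ULN is a DLT, while the same subject at 6 x ULN meets neither liver route. With entry ALT up to 2.5 x ULN, that second subject must stop treatment immediately. If no other row applies, the event drops out of the mTPI numerator. Section 11.9.4 expects mTPI to be the primary criterion for escalation, and DLTs are part of the Part 1 primary endpoint. The SAP's DLT displays (Table 3.65, Listing 61) show only events recorded as DLTs, so they cannot reveal an event that the definition missed.

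**Working it through.** **1. Which rows could still apply.** Take ALT above 5 x ULN, bilirubin below 2 x ULN, symptoms, and onset inside the window. The bilirubin route fails and the 3-5 x ULN route fails. The Grade 4 row fails if Grade 4 starts higher (assumption). The judgement row is written for toxicity after Day 21; it might be used if the event persists, but it does not clearly cover onset inside the window. That leaves the 80% row.

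**2. When the 80% row fails.** Fraction = doses received up to the last-dose day / scheduled doses in Days 1-21. The documents allow more than one schedule. Section 4.2.4.7 implies a gap from Day 2 until Day 4. The PK footnote to Table 9 puts the next dose on Day 3.

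| Schedule | Last dose Day 16 | Day 17 | Day 18 |
|---|---|---|---|
| Daily, 21 doses | 16/21 = 76.2% | 17/21 = 81.0% | 18/21 = 85.7% |
| Day 1, then Day 3 on, 20 doses | 15/20 = 75.0% | 16/20 = 80.0% | 17/20 = 85.0% |
| Day 1, then Day 4 on, 19 doses | 14/19 = 73.7% | 15/19 = 78.9% | 16/19 = 84.2% |
| BID, 42 doses | 32/42 = 76.2% | 34/42 = 81.0% | 36/42 = 85.7% |

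Table 1 asks for at least 80%, so the event goes uncounted from Day 17 (Day 18 on the 19-dose schedule) to Day 21. That is 5 (or 4) of 21 days. A stop at the nominal Day 15 draw gives at most 15/21 = 71.4% and is caught.

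**3. Reproducing Figure 4-1.** The target is 0.30 with 0.05 either side; Section 4.2.3 assumes "the true underlying toxicity rate for GSK3326595 falls within the range from 25% to 35% and centered at 30"%. The unit probability mass is the posterior probability of an interval divided by its length. I assumed a Beta(1,1) prior and a 0.95 exclusion cut.

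- 1/3, posterior Beta(2,3): Escalate 0.2617/0.25 = 1.05; Stay (0.4370 - 0.2617)/0.10 = 1.75; De-escalate 0.5630/0.65 = 0.87. Stay.
- 0/3, posterior Beta(1,4): Escalate 0.6836/0.25 = 2.73; Stay (0.8215 - 0.6836)/0.10 = 1.38; De-escalate 0.1785/0.65 = 0.27. Escalate.

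The same calculation matched all 195 cells checked (rows 0 to 6, up to 30 subjects).

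**4. Effect of one missing event.** If the subject is kept as a non-DLT, or is replaced by someone without a DLT, the count falls by one and the denominator is unchanged.

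| Event counted | Event missing |
|---|---|
| 1/3 Stay | 0/3 Escalate |
| 2/3 De-escalate | 1/3 Stay |
| 2/6 Stay | 1/6 Escalate |
| 4/6 De-escalate and exclude | 3/6 Stay |

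Not every count is sensitive: 1/6, 3/6, 3/9 and 4/9 lead to the same action either way. If the subject is replaced and the replacement has a DLT, the count is restored. At a true rate of 25-35%, a replacement is DLT-free with probability 1 - 0.35 = 65% to 1 - 0.25 = 75%.

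**The case against.** **The pointer to Section 5.4.5.** It sits inside the definition cell, and the text below says that Table 1 gives no management guidance. It could therefore be read as importing the stopping criteria, which would close the main gap for subjects with entry ALT up to 2.5 x ULN. That may have been the intent. But the definition refers to criteria listed in Table 1, the following text sends the reader to 5.4.5 for management, and Part 3 names the stopping criteria outright where they are meant to count. The wording is ambiguous at best.

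**Replacement.** A reader might infer that such a subject is certainly replaced. The documents do not settle this. Section 4.2 points to replacement, while Section 4.2.2 and footnote c would keep a subject who reached 80% and stopped for toxicity. With a last dose on Day 21, all window doses have been taken and replacement is doubtful. On either reading the event is not counted.

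**Other safeguards.** These stand.
- Section 4.2.4.5 requires review of all adverse events and laboratory data before each decision.
- Section 4.2.4.3 caps the next increment at 50% after a Grade >2 toxicity. This adds little from 400 mg up, where the planned steps (600, 800, 1200 mg) are already no larger.
- Liver stopping events go to the sponsor within 24 hours.
- A symptomatic ALT measured at 3-5 x ULN on the way up or down inside the window is itself a DLT.
- Scheduled draws mostly miss the uncovered days. The case needs an unscheduled draw, a Day 15 draw slipping to Day 17, or a Week 4 draw taken on Day 20 or 21.

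**Conclusion.** The point holds as a narrow defect in the literal Part 1 DLT rule. It rests on three assumptions: the CTCAE v4 Grade 4 ALT cut-off lies above 5 x ULN, the in-cell pointer does not add a DLT criterion, and the event begins inside the window. It then affects subjects whose last dose falls in the final 4 to 5 of 21 days, and it matters only at counts next to a Figure 4-1 boundary. The documents do not say how often such events occur.

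Two stronger readings are not supported. One is that symptomatic ALT above 5 x ULN generally escapes the DLT count: for most of the window the forced stop leaves the subject below 80%, and the event counts. The other is that the selected dose is unsafe or was wrongly chosen: nothing shows that such an event occurred. The 400 mg RP2D chosen on 21 March 2018 rested on safety, tolerability, efficacy, PK and PD (Section 4.3.2), and recruitment has ended. What remains is how Part 1 DLTs are reported and any reuse of the definition. Low priority.

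**What to change.** **For any reuse of Table 1**, make one of two one-line changes.

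- Delete the upper limit: ALT at or above 3 x ULN, bilirubin below 2 x ULN, with hepatitis symptoms or rash. This removes the anomaly directly.
- Or add the Part 3 line, so that any event meeting the Section 5.4.5 liver stopping criteria is also a DLT. This is wider, because it also counts asymptomatic ALT of 5 x ULN or more (entry ALT up to 2.5 x ULN). It leaves a remnant for high-baseline subjects: with entry ALT of 4.5 x ULN, a symptomatic 5.5 x ULN is not a stop, since 1.5 x 4.5 = 6.75.

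Do not add a 1.5 x baseline condition to the existing route. It would stop counting events that Table 1 counts now, such as entry 4.5 and a symptomatic 4.6 x ULN.

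**At final analysis**, compare Listing 61 with Listings 62 and 63, using the onset times planned in SAP Section 8.5.5. Report any Part 1 liver stopping event on Days 1-21 not recorded as a DLT. For each, state whether the subject was replaced and whether a Figure 4-1 action would have differed. Listings 10 and 20 cover high-baseline subjects who met no stopping rule. Do not redefine past DLTs.

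**Cost:** one line of text and one cross-check of planned listings, with no new data. If nothing is found, one sentence in the report closes the point.

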4.2.4.2. Non-Limiting Toxicities

The following toxicities have been deemed to be non-serious for the purposes of this study. These toxicities will not be taken into account for dose escalation decisions unless, in the opinion of the investigator and the GSK Medical Monitor, they represent a dose-limiting toxicity. For all other toxicities and their management, see Appendix 2.

- Grade 2 or less:
 - o Fatigue
 - o Rash
 - o Alopecia
- Grade 3 or less nausea, vomiting, or diarrhea controlled within 24h
- Electrolyte imbalance or other laboratory abnormalities controlled within 24h

4.2.4.3. Maximum Dose Increment

Built-in safety constraints are in place to prevent exposing subjects to undue risk of toxicity. The maximum allowable dose increment will be determined based on the prior dose level data. The permitted dose increments are a protocol-defined maximum; a smaller increment may always be used based on the decision of the investigators and medical monitor (Section 4.2.4.5). Planned dose levels are detailed in Section 4.2.4.4.

For each individual dose escalation step:

If no grade ≥ 2 non-hematologic non disease-related toxicity (except those listed in Section 4.2.4.2) is observed at the current dose, the dose increment will be no more than 100% of the current dose.

If one or more grade > 2 non-hematologic non disease-related toxicity (except those listed in Section 4.2.4.2), grade > 2 anemia or thrombocytopenia, or DLT is observed, the dose increment to the immediate next dose level will be no more than 50% of the current dose.

4.2.4.4. Planned Dose Levels

Projected daily dose levels are 12.5 mg, 25 mg, 50 mg, 100 mg, 200 mg, 400 mg, 600 mg, 800 mg, and 1200 mg. BID dosing may divide this total daily dose into two equal doses, administered twice daily. Additional doses (either lower than 12.5 mg, higher than 1200 mg, or intermediate doses between those listed above) and schedules may be explored based on emerging safety, PK, and PD data.

4.2.4.5. Dose Escalation Decisions

The GSK medical monitor, in joint discussion with the participating investigators, will be responsible for determining whether dose escalation during Part 1 should continue as

recommended by the mTPI approach. Prior to the dose escalation decision, the medical monitor, clinical scientist, safety physician, clinical pharmacologist, and investigators will review critical safety data defined in the Dose Escalation Plan, including data on all adverse events including non-DLT toxicities, laboratory assessments and other safety evaluations, as well as PK and PD data. The quality review of critical safety data will be described in the Dose Escalation Plan, which includes ongoing study monitoring visits along with data review of the clinical database.

The dose-escalation decision and rationale for each cohort will be discussed with investigators during teleconference(s) and documented in writing with copies maintained at each study site and in the master study files at GlaxoSmithKline (GSK).

4.2.4.6. Alternative Dosing Schedules

Alterations may be made to the schedule of administration and/or PK/PD sampling schedule based on the results of emerging PK and safety data.

Schedules that incorporate a recovery period may be explored (e.g., 3 weeks on, 1 week off). This approach will be considered if the safety and PK data suggest that a therapeutic exposure cannot be achieved using the initial schedule without excessive toxicity. The starting dose for the alternate schedule will be the highest completed dose level (at or below MTD) with the initial schedule. Escalation can then proceed as described in Section 4.2.3.

Schedules that use a different daily regimen (e.g., twice daily [BID] dosing) may also be explored. This approach will be considered if the safety, PK, and PD data suggest that a sufficient therapeutic exposure cannot be achieved using the initial schedule. If a shorter recovery period is used, the initial dose level will be $\leq 50\%$ of the highest completed dose level (at or below MTD) with the initial schedule. Escalation can then proceed as described using in Section 4.2.3. If BID dosing is to be utilized, study events will occur as detailed in Table 11 and Table 12.

The dosing schedule may also be adjusted to expand a prior dose cohort to further evaluate safety, pharmacokinetic and/or pharmacodynamic findings at a given dose level, or to add cohorts to evaluate additional dose levels. The study procedures for these additional subject(s) or cohort(s) will be the same as that described for other study subjects.

Any changes to the dosing schedule may be made only after review of all available data and clearance by the GSK medical monitor. Any planned changes will apply to a cohort of subjects and not an individual subject. Changes will be communicated to the site in writing along with justification and data supporting the change. A modified SRM, including updated Time and Events Table, will be provided to the sites prior to initiation of the alternative regimen.

4.2.4.7. Intra-subject Dose Escalation

In Part 1, intra-subject dose escalations may be considered on a case-by-case basis, provided that the subject has completed at least the DLT observation period without

 \geq Grade 2 non disease-related toxicity in the first 21 days of therapy, that all subjects at the next highest dose level have completed the DLT observation period, and that prior approval has been obtained from the GSK Medical Monitor. Subjects may be dose-escalated to the highest cleared dose. Individual subjects may dose-escalate multiple times provided that the above criteria are met at each intra-subject dose escalation step. Safety assessments from these subjects will be included in the MTD determination.

Subjects approved for intra-subject dose escalation will initiate daily dosing from Day 1 of the higher dose (i.e., no dose interruption from Day 2 until Day 4) and will require additional PK sampling on Day 15 at the higher dose, as specified in Time and Events table (see Section 8.1). Additional safety assessments may be specified at the time of dose escalation or schedule modification based on the safety profile in previous subjects at the higher dose level. Intra-subject dose escalations or schedule modification will be discussed with investigators and approved by the GSK Medical Monitor and safety monitoring required will be specified in writing.

